10.5. Detailed Description of the Multiple Imputation Procedure

The following is a detailed description of the multiple imputation procedure which will be used for analysis of the secondary efficacy endpoints.

In general, the missing pattern is anticipated to be not monotone, a two-step approach will be used:

- Step 1: the MCMC method will be used in conjunction with the IMPUTE=MONOTONE option to create an imputed data set with a monotone missing pattern. Set the SEED=17100 option in SAS MI procedure
- Step 2: Using the monotone data set from step 1, missing data will be imputed using the regression method. Set the SEED=34200 option in SAS MI procedure

The imputation model for step 1 will include the values of the analyzed parameter at baseline and planned time-points up to week 24.

The imputation model for step 2 will include the same variables as in step 1 with the following additional variables:

- age, BMI, and gender (age and BMI included as continuous variables).

Non-continuous variables included in the imputer's model (i.e., gender) are not expected to be missing.

In addition, for continuous efficacy variables anticipated to have a non-normal distribution (i.e. TG and Lp(a)), data will be log-transformed before imputation process and then back-transformed to create the imputed data sets using the TRANSFORM statement of SAS MI procedure.

For variables other than those continuous efficacy variables anticipated to have a non-normal distribution (i.e. TG and Lp(a)), for each simulation leading to negative imputed value, another value will be redrawn using MINIMUM option of SAS MI procedure.

The number of imputations (100) will be informally verified by replicating sets of 100 imputations and checking whether the combined results are stable. If not stable, the number of imputations will be increased and informally checked as above, and thus continued until stable estimates are obtained.

10.6. Detailed Description of Pattern Mixture Model

As the primary analysis of the primary efficacy endpoint (i.e., percent change from baseline to week 24 in calculated LDL-C for Part B), a pattern-mixture model approach will be used with a different imputation strategy applied for missing calculated LDL-C values during the on-treatment period (i.e., within the time period from the first study treatment administration up to the day of the last study treatment administration +35 days or to the day before the first long-term extension treatment administration, whichever comes first for Part B) and missing LDL-C values after treatment discontinuation (i.e., after the day of last study treatment administration +35 days in Part B) based on the following assumptions:

- Patients within 35 days of their last study treatment administration in Part B would continue to show benefit from treatment similar to that observed at the scheduled time point. Therefore, calculated LDL-C values missing during the on-treatment period will be considered “Missing at Random” and imputed using a model estimated using all samples collected on treatment.
- Patients who stopped taking their study treatment no longer benefited from it in the future, and thus tended to have calculated LDL-C values returning to baseline. Thus calculated LDL-C values missing after treatment discontinuation will be imputed based on patient’s own baseline value.

The assumptions for this approach are based on the following considerations:

- Missing values during the on-treatment period are mostly consecutive to:
 - Visits performed outside of the pre-specified time-window
 - No blood sample available although visit was done
 - LDL-C not measurable due to technical reasons

In addition, these missing data are often intermittent, i.e., followed by LDL-C values collected at subsequent visits. It is therefore considered reasonable to assume that these missing data were “At Random”.

Missing LDL-C values will be imputed 100 times to generate 100 complete data sets. The percent change from baseline to week 24 will be derived from observed and imputed LDL-C at this time point. The completed data sets will be analyzed using the SAS MEANS procedure. The results from the 100 analyses will be combined using Rubin’s formulae. If necessary, the number of imputations (100) will be increased until stable estimates are obtained.

Imputation of missing data during the on-treatment period

Missing LDL-C values during the on-treatment period will be imputed from other on-treatment measurements assuming Missing At Random, using SAS® MI procedure.

Only LDL-C values collected during the on-treatment period will be included in the imputation model. This way, missing LDL-C values during the on-treatment period will be imputed based solely on observed on-treatment LDL-C values.

The imputation model will include baseline LDL-C value, and all LDL-C values at pre-specified visits. Since the pattern of missing data will necessarily be non-monotone, a Monte-Carlo

Markov Chain (MCMC) method will be used. A minimum value of 0 will be specified in order to avoid negative imputed LDL-C values.

A sample SAS code is provided below:

```
proc mi data=DATAIN out=DATAOUT nimpute=100 minimum=. 0 0 0 0 0 0 0 0 0 0  
SEED=17100;  
var LDL_BASE LDL_W1 LDL_W2 LDL_W4 LDL_W8 LDL_W12 LDL_W16 LDL_W20  
LDL_W24;  
run;
```

As stated above, the input dataset DATAIN will include only LDL-C values collected during the on-treatment period. Any LDL-C values collected during the post-treatment period will be excluded from the input dataset. In practice, the MI procedure will generate imputed values for all missing values (whether on-treatment or post-treatment), but only imputed values during the on-treatment period will be kept in the final datasets that will be analyzed. Imputed values during the post-treatment period will be discarded and replaced by imputed values described in the next paragraph.

Imputation of missing data after treatment discontinuation

Missing LDL-C values during the post-treatment period will be imputed assuming LDL-C values would on average return to baseline values.

For each patient, missing post-treatment LDL-C values will be imputed 100 times, using a random draw from a normal distribution (SEED=34200), with mean equal to patient's own baseline value and variance equal to the conditional variance at the specific time-point, given the baseline value.

Let Y_0 and Y_1 denote the LDL-C at baseline and at the specific time-point respectively. Since Y_0 and Y_1 are assumed to have a bivariate normal distribution, the conditional variance of Y_1 given Y_0 is:

$$Var(Y_1|Y_0 = y_0) = \sigma_1^2(1 - \rho^2)$$

Where σ_1^2 denotes the variance of Y_1 and ρ the coefficient of correlation between Y_0 and Y_1 .

The conditional variance will be estimated from observed data at the specific time-point.

During the random generation process, a minimum value of 0 will also be applied in order to avoid negative imputed LDL-C values.

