14. At weeks 8 and 16 of the follow-up period all patients will be contacted by phone to query LMT compliance, to inquire about AEs or changes to concomitant medications, confirm required contraception use, and remind patients of pregnancy reporting. Sexually active females of childbearing potential will report the results of their home pregnancy test. For patients who decide to enter a compassionate use or early access program, the EOT visit will be their last visit and they will forgo the 24-week follow-up period.
15. Overlapping assessments completed at the EOT visit of Part A or Part B do not need to be duplicated during visit 1 of Part C. Part C visit 1 should occur on the same day as Part A visit 11 or Part B visit 11. All necessary assessments are listed in the applicable SOE (Part A or Part B) column for visit 11.
16. Patient can only receive the dose once all assessments from Part A or Part B Visit 11 are completed.
17. For patients who decide to enter a CUP or EAP, the EOT visit will be their last visit and they will forgo the 24-week follow-up period.

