3.1.2. Modified Intent-to-Treat (mITT)

The modified ITT (mITT) population is defined as all patients who received at least 1 dose or part of a dose of open-label study drug in Part B and have an evaluable primary efficacy endpoint. The endpoint is considered as evaluable when both of the following conditions are met:

1. Availability of at least 1 measurement value for calculated LDL-C before first dose of study drug (i.e., baseline).
2. Availability of at least 1 calculated LDL-C value during the efficacy treatment period and within one of the analysis windows up to week 24. The efficacy treatment period is defined as the time from the first study drug administration up to 35 days after the last study drug administration in Part B.

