5.7.1. Analysis of Primary Efficacy Variable for Part B

While applying the ITT estimand, the percent change from baseline in calculated LDL-C at week 24 will be descriptively summarized for all patients in the ITT population using mean, SE, and 95% CI. Missing data will be imputed using a pattern mixture model (PMM) approach as described below (see Appendix 10.6 for more details).

In the PMM approach, different imputation strategies will be applied to calculated LDL-C values missing during the on-treatment period (i.e., within the time period from the first study treatment administration up to the day of last study treatment administration +35 days in Part B) versus calculated LDL-C values missing due to treatment discontinuation after the on-treatment period (i.e., after the day of last study treatment administration +35 days in Part B) based on the following assumptions:

- Patients within 35 days of their last study treatment administration in Part B would continue to show benefit from treatment similar to that observed at the scheduled time point. Therefore, calculated LDL-C values missing during the on-treatment period (e.g., samples obtained out-side the specified window for apheresis, no blood sample available although visit was performed, etc.) should be considered “Missing at Random” and imputed based on other observed measurements in the on-treatment period.
- Patients who stopped taking their study treatment in Part B no longer benefited from it after discontinuation, and thus tended to have calculated LDL-C values returning to baseline. Therefore, calculated LDL-C values missing after the on-treatment period should be imputed based on patient’s own baseline value.

Missing data from the ITT population will be imputed 100 times to generate 100 complete data sets, using the SAS MI procedure (using Markov Chain Monte Carlo). The 100 completed datasets of observed and imputed calculated LDL-C data will be used for the primary analysis.

For the percent change from baseline calculated LDL-C endpoint, the 100 complete datasets of observed and imputed calculated LDL-C data at week 24 will be analyzed using the SAS MEANS procedure. The SAS MIANALYZE procedure will be used to generate valid statistical inferences by combining results from the 100 analyses using Rubin’s formulae. Combined estimate for mean at Week 24 will be provided with the standard error (SE) and 95% confidence interval (CI). Formal statistical testing is not planned.

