5.8.3. Clinical Laboratory Measurements

The following definitions will be applied to laboratory parameters:

- Part A treatment and observation period: the period used for quantitative analysis for Part A is defined from the day after the first study treatment administration to the day of last visit during the Part A observation period.
- Part B treatment period: the treatment period used for quantitative analysis is defined from the day after the first study treatment administration to the day of the last study treatment administration + 28 days for those patients not proceeding into Part C, or up to the day of the first study treatment administration in Part C for those patients proceeding into Part C.
- Part C treatment period: the treatment period used for quantitative analysis is defined from the day after the first study treatment administration in Part C to the day of the last study treatment administration in Part C + 28 days.
- Pooled treatment period: for Part A patients, the treatment period used for quantitative analysis is defined from the day after the first study treatment administration in Part C to the day of the last study treatment administration in Part C + 28 days. For Part B patients, the treatment period used for quantitative analysis is

defined from the day after the first study treatment administration in Part B to the day of the last study treatment administration in Part C + 28 days or to last study treatment administration in Part B + 28 days for patients not entering into the Part C.

For respective treatment period, clinical laboratory parameter actual values (quantitative) and change from baseline values will be descriptively summarized at baseline and each post-baseline visit by at least patient number, mean, median, Q1, Q3, SD, minimum and maximum. Clinical laboratory parameters mean changes from baseline, with the corresponding SE, can be plotted at each visit in the case results warrant further investigation. These parameters will be presented by the biological functions defined in Section 4.8.2. For glucose, only fasting samples will be included in the summaries.

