10.2. Windows for Analysis Time Points

Below are the definitions for the visit windows programmatically imposed on measures repeatedly collected over the course of the study. These visit windows reflect the study schedule of assessments as described in the protocol.

The visit windows are constructed using ranges applied to the number of days in study (study days) when the measure is collected. Below are the relevant definitions for the analysis visit windows:

1. Study day is defined as the number of days since the first study treatment administration +1. The first study treatment occurs on Study Day 1.
2. Part C study day is defined as the number of days since the first Part C study treatment administration+1
3. Since the protocol specifies that measurements be collected before study treatment is administered on a given day, it is appropriate that baseline include Day 1.

Table 1: Global Analysis Windows for Part A

Visit label	Targeted Study Day	Analysis Window in Study Day
Baseline	1	Measurement obtained closest to first study treatment, while remaining prior to first study treatment
Week 1	8	2 to 11
Week 2	15	12 to 18
Week 3	22	19 to 25
Week 4	29	26 to 35
Week 6	43	36 to 49
Week 8	57	50 to 63
Week 10	71	64 to 77
Week 12	85	78 to 98
Week 16	113	99 to 140
FU- W8	For patients prematurely discontinued Part A: EOT visit study day + 56 days For patients completed Week 16 visit: 169	For patients prematurely discontinued Part A: EOT visit to 84 days after EOT visit For patients completed Week 16 visit: 141 to 196
Study days are calculated from the day of first IMP infusion, the day of first IMP infusion being Day 1.		

Table 2: Global Analysis Windows for Part B

Visit label	Targeted Study Day	Analysis Window in Study Day
Baseline	1	Measurement obtained closest to first study treatment, while remaining prior to first study treatment
Week 1	8	2 to 11
Week 2	15	12 to 21
Week 4	29	22 to 35
Week 6	43	36 to 49
Week 8	57	50 to 70
Week 12	85	71 to 98
Week 16	113	99 to 126
Week 20	141	127 to 154
Week 24	169	155 to 196
FU- W8	For patients prematurely discontinued trt: last study trt + 84 days For patients completed Part B trt period: 225	For patients prematurely discontinued trt: 56 to 97 days after last trt For patients completed Part B trt period: 197 to 238

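### The pattern-mixture appendices end the Part B on-treatment period the day before the first Part C dose, so a same-day roll-over's week-24 LDL-C is left out of the imputation model

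*SAP*

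**What the plan says.** **Main text.** The Protocol synopsis (Statistical Plan), Protocol 11.4.3.1 and SAP 5.7.1 run the on-treatment period "up to the day of last study treatment administration +35 days in Part B". The mITT efficacy treatment period in Protocol 11.3.1 and SAP 3.1.2 likewise runs "up to 35 days after the last study drug administration in Part B". None of these five places cuts the period at the start of Part C.

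**Appendices.** SAP 10.6 and Protocol Appendix 1 give the same 35 days and then add "or to the day before the first long-term extension treatment administration, whichever comes first for Part B".

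**Roll-over timing.** Protocol 9.1.1.3, footnote 15 to Table 3, says: "Part C visit 1 should occur on the same day as Part A visit 11 or Part B visit 11". Protocol 6.1 and SAP 2.3 say only that the two visits can coincide. Footnote 16 fixes the order on the day: "Patient can only receive the dose once all assessments from Part A or Part B Visit 11 are completed".

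**Use of the data.** SAP 10.6 and Appendix 1 admit only on-treatment LDL-C values to the input of the SAS MI procedure, while their sample code lists LDL_W24 as a model variable. The primary mean is taken over observed and imputed week-24 values, under the treatment-policy estimand of SAP 4.7.1.

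**The concern.** Whether a value counts as on-treatment decides whether it helps to estimate the imputation model. A same-day roll-over's week-24 sample is drawn before the Part C dose and about four weeks after the last Part B dose. The main text counts it as on-treatment; the appendix does not. Read literally, the appendix removes the most relevant week-24 data from the model that imputes week 24. If every patient rolled over that way, LDL_W24 would have no observed values in the model at all.

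This also conflicts with the appendix's own premise that patients within 35 days of the last dose still benefit and are imputed from on-treatment samples. The same approach serves non-HDL-C, TC and Apo B (SAP 5.7.2.1), the responder endpoint (SAP 5.7.2.3), the subgroups (SAP 5.7.1.2) and the by-visit summaries (SAP 5.7.3). Two readings of a primary imputation rule leave a choice open in an open-label trial.

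**Working it through.** The plan has no sample-size or precision figure to reproduce (Protocol 11.2).

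**1. Day arithmetic.** Inputs from Protocol Table 2: week-20 dose on day 141, week-24 visit on day 169, each ±3 days. Assume the first Part C dose is on the week-24 day.

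- Main-text end: 141 + 35 = day 176. The day-169 sample is in.
- Appendix end: min(176, 169 − 1) = day 168. The sample is out.
- Dose days 138, 141, 144 crossed with visit days 166, 169, 172: the main-text end is day 173 to 179 (sample always in) and the appendix end is day 165 to 171 (always out).

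Limits: the visit falls 166 − 144 = 22 to 172 − 138 = 34 days after the dose under these windows. Under the ±7-day dosing window of Protocol 8.1 it can be 172 − 134 = 38 days. After a skipped week-20 dose it is 169 − 113 = 56 days. In those two cases the sample lies outside both definitions, so the conflict does not arise.

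**2. What changes.** If no week-24 value is missing, the primary mean is the same under both definitions. If one is missing, it is imputed from a week-24 model without the same-day roll-overs' values. By-visit summaries can also change when an earlier value is missing, because week 24 is a variable in the same model. The MMRM analyses are not touched: the ITT version uses all values in the windows (SAP 5.7.1.1) and the on-treatment version uses the untruncated mITT period.

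**3. Residual degrees of freedom for week-24 LDL-C.** Coefficients: intercept, baseline and weeks 1, 2, 4, 8, 12, 16, 20 = 9. Suppose one week-24 value is missing, everything else is observed, and k other patients roll over on the same day.

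- N = 14 (Protocol 11.2): (13 − k) − 9 = 4 − k, that is 4, 3, 2, 1, 0 for k = 0 to 4.
- N = 18 (still in SAP 2.2): (17 − k) − 9 = 8 − k.
- Apo B is scheduled only at baseline and weeks 4, 8, 12 and 24, so there are 5 coefficients: 13 − 5 = 8 before any exclusion at N = 14.

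**4. Added noise, LDL-C, N = 14.** For least squares with 8 jointly normal predictors and n observed rows, expected prediction variance divided by residual variance is (1 + 1/n)(n − 2)/(n − 10).

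| k | n | Ratio |
|---|---|---|
| 0 | 13 | 3.95 |
| 1 | 12 | 5.42 |
| 2 | 11 | 9.82 |
| 3 | 10 | not finite |

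The error that one imputed value brings to the primary mean is SD × √ratio / 14. The residual SD is not in the documents; assume 10 percentage points (range 5 to 15).

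- k = 0: 10 × √3.95 / 14 = 1.4 points (0.7 to 2.1).
- k = 2: 10 × √9.82 / 14 = 2.2 points (1.1 to 3.4).

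This is a least-squares approximation, not the specified MCMC run with its minimum of 0.

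**The case against.** The main text sends the reader to the appendix for details, so the appendix may be the operative rule and the main text its summary. The clause has a purpose: it keeps samples taken after the first Part C dose out of Part B data. A day-before cut-off is also used elsewhere, for concomitant medications (SAP 4.3) and adverse events (SAP 4.8.1). A missing week-24 value should be uncommon in a same-day roll-over, because the visit's assessments come before the dose. And nine variables on 14 patients make a thin model even without the clause.

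Most of this stands as a limit on size. It does not remove the contradiction. Adverse-event and medication periods have no pre-dose sample to preserve, whereas the Part B laboratory period in SAP 5.8.3 runs "or up to the day of the first study treatment administration in Part C for those patients proceeding into Part C". SAP 10.2 applies the pre-dose argument to baseline ("measurements be collected before study treatment is administered on a given day, it is appropriate that baseline include Day 1"), although SAP 6.1 words baseline as before the date of first dosing. The SAP's boundary conventions are mixed, so none of them settles the matter.

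Three stronger readings are tempting and not supported:

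- That roll-overs' week-24 values are lost from the primary analysis. They are not; observed values are used whatever the period.
- That a roll-over's missing week-24 value would be drawn around baseline. SAP 10.6 reserves that for patients who stopped treatment and are past 35 days from the last dose. Days 169 to 176 fall literally in neither class, but the stated assumptions point to missing at random.
- That most patients are affected. No roll-over rate is given, the visits need not coincide, and Protocol 11.4.3.3 allows for prolonged gaps before Part C.

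**Conclusion.** The concern holds as an inconsistency in the primary imputation rule that should be fixed before database lock. For same-day roll-overs, the appendices exclude from the missing-at-random model a pre-dose week-24 value that the main text counts as on-treatment.

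The effect on the primary estimate is zero if no week-24 value is missing. With one missing at N = 14, each other same-day roll-over costs one of 4 residual degrees of freedom, and none is left at four. Under the assumed SD of 10 points, two such exclusions raise the error from that value from about 1.4 to 2.2 points, an increment of 0.8. This is extra imputation noise or, at the extreme, a model that cannot be estimated. No bias is shown. The figures rest on nominal visit days, otherwise complete data and the least-squares approximation.

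**What to change.** Put one definition in all seven places: the Protocol synopsis, Protocol 11.3.1, 11.4.3.1 and Appendix 1, and SAP 3.1.2, 5.7.1 and 10.6. Suggested content: the on-treatment period ends at the last Part B dose plus 35 days or at the first Part C dose, whichever is first, and samples taken before the dose on that day are included.

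Do not simply delete the clause. Samples taken after the first Part C dose (days 170 to 176 on nominal days) could then count as Part B on-treatment values.

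In SAP 10.6 and Protocol Appendix 1, also state that a missing week-24 value within 35 days of the last Part B dose, in a patient continuing into Part C, is imputed as missing at random. Say which date classifies a missing value, since the documents give none.

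The cost is one common sentence in seven places and two clarifying sentences in the two appendices. No new data and no change to visits are needed.
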